7.7.2 Hypoglycemia

- Three sources were included in this study for evaluation of safety focused on identifying important hypoglycemia: Adverse event reporting

Adverse event reviews included specifications for blinded safety reviews (as described in safety review plan) with attention for identifying important hypoglycemia and specifications for medical monitoring also targeting hypoglycemia.

- Central Laboratory data

Ongoing blind data review included targeted identification of values in ranges for very low (<54) and low (between 54 and 70) as reported by the laboratory data file from the core laboratory.

- Continuous glucose monitoring (CGM)

The CGM data were included in the blind data reviews (consistent with ICH E9 guidance) with targeted identification of values in ranges for very low (<54) and low (between 54 and 70) as reported in the datafiles from the CGM sources.

7.7.3 Vital Signs

Vital signs (pulse rate, blood pressures, and weight) will be summarized by Pre-dose, Day 1 and mean values and mean change from baseline to each visit.

Clinically important values or changes in vital signs will be examined with summary tables and supportive listings for subjects meeting the criteria for values or changes of potential clinical concern (located in Section 13 of this SAP).

7.7.4 Clinical Laboratory Measurements

Because “exacerbations” of pre-existing abnormalities in laboratory analytes are examined using clinical judgment and are reported as TEAEs, additional analysis on TEAVs is limited to subjects with values that are normal prior to dosing and abnormal after dosing.

Adverse events of special interest also treatment-emergent abnormal values (TEAVs) in laboratory parameters related to liver function tests, specifically ALT, AST, bilirubin, and ALK.

Potentially clinically significant values in laboratory analytes will be examined in accordance with the table of values or changes of potential clinical significance in this SAP. Proportions of subjects in each treatment group who meet the criteria will be analyzed.

Laboratory data will be summarized by Baseline and change from Baseline to each scheduled assessment time with descriptive statistics.

Liver function tests have additional monitoring for this study.

To explore the potential for drug-induced liver injury consistent with *Guidance for Industry “Drug-induced liver injury: premarketing clinical evaluation”* (CDER, CBER, July 2009), subjects will be summarized and listed who meet the following criteria:

- (1) Elevations in either AST or ALT of at least 3-times the upper limit of normal, and

- (2) An accompanying abnormal bilirubin.

Additionally, a summary and listing will be examined for subjects with elevations in either AST or ALT of at least 3-times the upper limit of normal, regardless of bilirubin.

7.7.5 Electrocardiography

Electrocardiography data will be summarized by Baseline and mean values and mean change from baseline to each assessment.

Corrections to QT intervals will be made by Fridercia's method. Categorical analysis will be done consistent with ICH E14, "Clinical evaluation of QT/QTc interval prolongation and proarrhythmic potential for non-antiarrhythmic drugs" (October 2005). Subjects will be categorized and summarized according to:

- Absolute QTc interval prolongation:
 - QTc interval > 450
 - QTc interval > 480
 - QTc interval > 500
- Change from baseline in QTc interval:
 - QTc interval increases from baseline > 30
 - QTc interval increases from baseline > 60.

For purposes of analysis, the baseline will be defined in two ways:

- Mean of triplicate values at baseline (so that the analysis for the groups and the individuals will be on change to each visit from the mean pre-dose triplicate measures value).
- Maximum of all pre-dose values (so that the analysis for the groups and the individuals will be on change to each visit from the worse pre-dose value).

An additional analysis will include change from the worst pre-dose value to the worst post-dose value.

7.8 Pharmacokinetics Analysis

Plasma trough concentrations of TTP399 will be summarized at each scheduled assessment time point with the following descriptive statistics: number of subjects (n), mean, standard deviation (SD), coefficient of variation (CV%).

7.9 Concomitant Medications

Concomitant medications will be coded and summarized using World Health Organization Drug Dictionary (WHO-DD).

8 Data Conventions

The following analysis conventions will be used in the statistical analysis.

8.1 Definition of Baseline

For safety evaluations, the baseline assessment for all measurements will be the mean of all pre-dose values that are considered to be valid taken prior to the initiation study double-blind medication

For HbA1c efficacy evaluations, the baseline measurement will be the average of the pre-treatment measures taken prior to initiation of double-blind study medication (first dose of double-blind study medication).

For CGM, the baseline measurement will be the average of the latest available days of CGM measures taken prior to initiation of double-blind study medication (first dose of double-blind study medication) and beginning with the first day of single-blind placebo study medication (first dose during placebo-run-in period), noting that there must be at least 10 days of CGM data to enable a meaningful average calculation. For insulin, the baseline measurement will be the average of the latest available days of insulin measures taken prior to initiation of double-blind study medication (first dose of double-blind study medication) and beginning with the first day of single-blind placebo study medication (first dose during placebo-run-in period).

For other efficacy evaluations, the baseline measurement will be the latest available (at least 10 days required), valid measurement taken prior to initiation of study medication (first dose).

8.2 Continuous Glucose Monitoring and insulin conventions

Continuous glucose monitoring (CGM) measures are automated by device. Insulin data are collected from InPen or pump devices (some of which is keyed) and curated by qualified data managers. It is noted that prescribed insulin is used for basal insulin, and recorded insulin is used for bolus.

Gaps may occur in either parameter. The following conventions will be used:

- There must be at least 10 days of data available to support any period calculation of summary statistics.
- Day 1 and Day 84 will not be used in any calculation of CGM or insulin.
- Other visit days will not be used, due to potential disruptions and likely gaps. An important note is that all CGM data will be included in the evaluation of hypoglycemia events.
- Data from shift workers (individuals who work outside of normal business hours) will not be used for CGM.
- Insulin data from days with pump failure will not be used.
- If there is a gap in the measure of more than 8 hours, the 24-hour period will not be used.
- If < 80% of the data are available, the measure will not be used.
- If blind review (done in accordance with ICH E9 guidance) identifies a gap for which inclusion of the day could be misleading, the day will not be used.
- If a glucose value exceeds 400 mg/dl, the event is examined blinded to treatment for evidence of significant deviation from the prescribed insulin regimen, and if blind review determines that there is likely significant deviation from the prescribed insulin regimen, the days CGM and insulin data will not be used.
- Device manufacturers for CGM have researched and documented that improvements in HbA1c as much as 1% can be observed within 3 months of beginning use of the CGM device. In this subject population in consideration for the mechanism of action for GKA, it is unexpected for a subject to experience changes in HbA1c of more than 1% in either direction. Any observed change of more than 1% will be queried to determine whether or not the use of the CGM began with the initiation of the study or whether there is some other medical explanation from the principal investigator that may reveal a major protocol deviation or a dramatic change that is not interpretable for protocol purposes. Blind review (done in accordance with ICH E9 guidance) will evaluate protocol suitability of the data, if there are explanations disallowed by the protocol; such

cases will be judged for appropriateness for use in the primary estimand. Multiple imputation based on recursive regression will be used to predict unusable data for the primary analysis (supportive analysis will be done using all available data).

- Significant holidays including Thanksgiving Day and Christmas Day are excluded from analysis of CGM.

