It is noted that strict application of the Hochberg methodology implies that rigorous p-values may not be applicable in the event of failure to reject either hypothesis in Evaluation 2. The intersection hypothesis is, however, applicable, and it is the intention of this analysis plan to continue testing under the intersection hypothesis and interpret p-values as rigorous as opposed to nominal.

Superiority on treatment response is evaluated:

- H_{02} : The proportion of treatment responders at Week 12 for the group treated with 800 mg TTP399 is equal to that of the placebo group.
- H_{12} : The proportion of treatment responders at Week 12 for the group treated with 800 mg TTP399 is not equal to that of the placebo group.

The study is declared to have met its primary endpoint if Evaluation 1 concludes TTP399 plus the modified regimen of insulin is noninferior to optimized insulin

And

Using the Hochberg method, either Evaluation 2 finds TTP399 is superior on HbA1c or Evaluation 3 finds TTP399 is superior on the proportion of treatment responders.

Conditional on achievement of endpoints, statistical evaluation continues.

Conditional Second Statistical Evaluation:

- **Evaluation 4:**

Superiority on daytime time in range is evaluated:

- H_{03} : The mean change in daytime time in range from baseline to Week 12 for the group treated with 800 mg TTP399 is equal to that of the placebo group.
- H_{13} : The mean change in daytime time in range from baseline to Week 12 for the group treated with 800 mg TTP399 is not equal to that of the placebo group.

Conditional Third Statistical Evaluation:

- **Evaluation 5:**

Superiority on time in hypoglycemia using 70 mg/dl as the threshold is evaluated:

- H_{04} : The mean change in time in hypoglycemia using 70 mg/dl as the threshold from baseline to Week 12 for the group treated with 800 mg TTP399 is equal to that of the placebo group.
- H_{14} : The mean change in time in hypoglycemia using 70 mg/dl as the threshold from baseline to Week 12 for the group treated with 800 mg TTP399 is not equal to that of the placebo group.

Conditional Fourth Statistical Evaluation:

- **Evaluation 6:**

Superiority on time in hypoglycemia using 54 mg/dl as the threshold is evaluated:

- H_{05} : The mean change in time in hypoglycemia using 54 mg/dl as the threshold from baseline to Week 12 for the group treated with 800 mg TTP399 is equal to that of the placebo group.

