For completeness, an observed cases analysis will be done by visit in which no data are excluded, no data are imputed, and no data are represented at times other than when they were observed. As an alternative for handling missing data according to the rules of the primary analysis, a supportive analysis will be done using last-observation-carried-forward (LOCF).

For statistical analyses, 95% confidence intervals will be produced for the least squares means (LSM) in each treatment group, as well as the LSM differences as compared to placebo. For MMRM and ANCOVA, two-sided p-values will be displayed for the comparison against placebo.

To ensure robustness of analysis conclusions against parametric assumptions, rank analogues will be executed as supportive analysis. If the PPS differs from the FAS by more than 10%, the analyses will be replicated on the PPS. If the PPS and the FAS do not differ by more than 10%, analysis may not be done on the PPS. Final judgments will be made at the blind data review meeting in accordance with ICH E9.

All analyses will be done using the intent-to-treat (ITT) principle.

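### CGM days are reviewed for insulin deviation only when glucose exceeds 400 mg/dl, so the endpoint's own value helps select the days behind the gated daytime time-in-range test; separately, shift workers' CGM data are dropped despite the FAS/ITT commitment

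*SAP*

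**What the plan says.** SAP 8.2 sets the conventions for which CGM and insulin days count. One of them reads: "If a glucose value exceeds 400 mg/dl, the event is examined blinded to treatment for evidence of significant deviation from the prescribed insulin regimen". If blinded review then finds a significant deviation likely, "the days CGM and insulin data will not be used". The section does not define a significant deviation. It gives no matching trigger for low glucose, or for deviation on days whose peak was 400 or less.

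The next relevant convention concerns people: "Data from shift workers (individuals who work outside of normal business hours) will not be used for CGM".

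Other conventions remove days for reasons unrelated to glucose level. Examples are "If there is a gap in the measure of more than 8 hours, the 24-hour period will not be used" and "Other visit days will not be used, due to potential disruptions and likely gaps". Days are also lost when blind review "identifies a gap for which inclusion of the day could be misleading, the day will not be used". Measures with under 80% of data, Day 1, Day 84 and major holidays go as well, and each period needs at least 10 usable days. The section also states that every CGM reading is kept for evaluating hypoglycemia events.

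These data feed the conditional test sequence in SAP Section 2. For Evaluation 4 it states: "Superiority on daytime time in range is evaluated". Evaluations 5 and 6 test time below 70 and 54 mg/dl. Time above 180 and 250 mg/dl and bolus insulin are secondary variables in SAP 6.1.2. SAP 7.6.2 assigns all secondary endpoints to the FAS under the ITT principle, and SAP 7.6.1 closes with: "All analyses will be done using the intent-to-treat (ITT) principle".

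**The concern.** A day is opened for inspection because its glucose was very high, and glucose is what the endpoint measures. Two days with the same insulin departure are treated differently: one peaking at 410 may be deleted, one peaking at 390 stays. Reviewers do not know the arm, but they do know the outcome.

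High glucose after an insulin departure is also something treatment could plausibly change. Protocol 8.11 has bolus insulin altered at the start of double-blind dosing and adjusted afterwards. SAP Section 2 says insulin modification on active treatment may itself differ because of TTP399. SAP 8.2 analyses prescribed rather than recorded basal insulin, so the analysed basal values cannot show a missed basal dose. Reviewers may then have to infer the departure from the excursion itself.

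The shift-worker rule raises a different problem. Part 2 eligibility (protocol 5.3) does not exclude shift workers, so they are randomized and can enter the FAS, yet they contribute nothing to any CGM endpoint. A fixed 6am-10pm day (SAP 7.6.3.1) could justify separating them for Evaluation 4. It gives no reason to remove them from measures that ignore the clock.

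SAP 8.2 states no analysis on all CGM days. The supportive analysis on complete data that it mentions belongs to the bullet on HbA1c changes above 1%.

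**Working it through.** **Plan figures.** SAP 1.9 gives no sample size for any CGM endpoint. Its HbA1c figure (SD 1%, difference 0.7%, two-sided alpha 0.049, 80% power) reproduces: the t-based solution is 33.2, rounded up to 34 per group, with power 0.809. The point does not rest on it.

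**Days available.** Protocol 7.3.5 and 7.3.10 require at least 13 days between the visits that bound each CGM period. Visit days are dropped, so:
- visits 13 days apart leave 13 - 1 = 12 full days, and 12 - 10 = 2 can be deleted before the 10-day minimum fails;
- visits 14 days apart leave 13 full days, and 3 can be deleted.

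One deletion more than that costs the patient the whole period.

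**Shift in one patient's mean.** Assumptions not in the documents: 12 days, other days at 55% time in range, a deleted day at 15-35%. Deleting k days raises the mean by k x (55 - bad day)/12.
- k = 1: (55 - 35)/12 = 1.7; (55 - 25)/12 = 2.5; (55 - 15)/12 = 3.3 points.
- k = 2: 3.3 to 6.7 points.

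**Effect on the arm comparison.** This is an illustrative simulation, and every input except the 45 per arm (SAP 1.7), the 10-day rule and alpha 0.049 is assumed. Each period has 12 days, and patient means centre on 60% (SD 12 between patients, SD 12 between days). A day above 400 costs 40 points, and its frequency varies between patients. Baseline frequency equals the placebo frequency. Review deletes a fixed share of such days, and patients left with fewer than 10 days are dropped. Change from baseline is compared by t-test over 2,000 runs per row.

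| Days above 400 on treatment (placebo / active) | Share deleted | Effect, all days | Effect after deletion | Rejection, all days | Rejection after deletion |
|---|---|---|---|---|---|
| 10% / 5% | 30% | 1.97 | 1.37 | 0.289 | 0.173 |
| 10% / 5% | 50% | 1.94 | 0.86 | 0.281 | 0.089 |
| 10% / 5% | 100% | 1.97 | 0.03 | 0.284 | 0.042 |
| 5% / 10% | 30% | -1.96 | -1.39 | 0.306 | 0.171 |
| 5% / 10% | 50% | -1.99 | -0.88 | 0.308 | 0.104 |
| 5% / 10% | 100% | -2.00 | -0.04 | 0.297 | 0.049 |

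With equal frequency in both arms (5% or 10%), rejection after deletion ran from 0.044 to 0.058 against 0.049 nominal. The Monte Carlo standard error is sqrt(0.049 x 0.951/2000) = 0.005.

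**Shift workers.** If 5-15% of patients are shift workers (assumption) and are simply lost, intervals widen by sqrt(1/0.95) = 1.026 to sqrt(1/0.85) = 1.085, that is 2.6% to 8.5%.

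**The case against.** Several stronger readings are tempting, and the documents do not support them.

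- **That 400 mg/dl is the only route to losing a day, or that every such day is lost.** Gaps, visit days, holidays and low completeness also remove days. A day above 400 goes only if blinded review also judges deviation likely. The word only holds for the insulin-deviation review.
- **That the shift-worker rule lets the outcome choose the data.** Shift work is a patient characteristic. It is a population question, except where a shift change occurs on treatment, which SAP 5.4 lists as an intercurrent event.
- **That the hypoglycemia tests are shown to be affected.** SAP 8.2 keeps all CGM data for hypoglycemia events. Whether events includes time below 70 and 54 mg/dl is not stated, so the effect on Evaluations 5 and 6 is unproven.
- **That alpha is inflated.** Review is blinded, Evaluation 4 is reached only after the primary succeeds, and simulated type I error held with equal frequencies. In the unequal scenarios the estimate moved toward zero.

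The best defence is the estimand. SAP Sections 3 and 5.4 treat major insulin deviation as an intercurrent event, so removing such data could be deliberate. That stands as a reason for excluding deviation days, although those sections are written mainly for HbA1c. It does not justify finding the days by the endpoint's own value.

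Two cautions on size also stand. The rule applies at baseline and Week 12 alike, so patient-level shifts can partly cancel in the change. SAP 7.5 generally uses multiple imputation for measures, so the interval widening holds only if shift workers are simply lost.

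**Conclusion.** The point holds in this form. The insulin-deviation review has a one-sided trigger set on the outcome, and it bears on Evaluation 4, the hyperglycemia variables and the bolus-insulin variable. The demonstrated harm is a distorted estimate and lost power when treatment changes how often glucose exceeds 400. A real benefit can be hidden, and so can a real worsening. A false-positive claim is not demonstrated.

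The size cannot be fixed from the documents, which do not say how often days exceed 400 with a deviation. Per patient, one deleted day is worth 1.7-3.3 points under the stated assumptions. In the simulated 10% versus 5% scenario, a 2.0-point benefit fell to 1.4, 0.9 or 0.0 as 30%, 50% or 100% of such days were deleted.

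The exclusion of shift workers is a separate inconsistency with the FAS/ITT statements. The HbA1c primary analysis is untouched by either rule. The change should be made, but it concerns gated and secondary endpoints.

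**What to change.** In SAP 8.2:

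1. In the main CGM analyses keep every day that meets the completeness rules, whatever the glucose level. Use the 400 mg/dl exclusion only in a sensitivity analysis. If deviation days are to be excluded, identify them from insulin records by criteria set in advance, regardless of glucose, and say how basal departures will be found when prescribed basal insulin is the analysed value.
2. Keep shift workers in measures that do not depend on the clock, including Evaluations 5 and 6 if these are 24-hour measures (the SAP should say so). Set them apart only for the 6am-10pm day/night split, with an all-FAS sensitivity analysis for Evaluation 4.
3. State whether the retention of all CGM data for hypoglycemia events covers time below 70 and 54 mg/dl.

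The cost is SAP wording and additional sensitivity runs on data already held. The downside is slightly more variability in the CGM endpoints.

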8.3 Invalid Data

Intensive data management efforts focus on identifying invalid data, providing queries to the investigator, and having the site resolve all issues so that it is not necessary for any data to be accommodated by the sponsor. However, in the unlikely event that data from ECG, vital signs, or other data sources are deemed to be highly improbable during blinded data review (done in accordance with ICH E9 guidance) that includes medical, clinical, and data management consensus, invalid will be set to missing. Examples include pulse rate and blood pressures values when changes in antihypertensive medications have been introduced or changes in lipid measurements in the presence of changes background medications for lipid control. Conventions for determination of invalid data will be made blinded to study treatment and documented in the Data Management Plan, the minutes to a blind data review meeting (done in accordance with ICH E9 guidance), in the study data tabulation model (SDTM) datasets, in the set of tables, figures, and listings (TFLs) appended to the clinical study report (CSR), or in the text of the CSR.

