6.10.2. Other Concomitant Medications

Any medication (prescription and over-the-counter medications) taken within 90 days prior to Screening, until the Follow-Up visit, must be recorded with indication, daily dose, and start and stop dates of administration. All patients will be questioned about concomitant medication at each clinic visit.

Medications or supplements prohibited or restricted at screening in exclusion criteria 5 should be similarly prohibited or restricted during the study. If during the study, the PI believes any of these medications are required or if a patient takes any of these medications during the study, the PI should contact the Sponsor for instructions on how to proceed.

Whenever possible, attempts must be made **not to** alter the doses and regimens of background medications or supplements (with the exception of insulin, as described above). Any changes made to background medications or supplements must be captured in the patient's CRF. Over-the-counter or prescription medications which are taken "as needed" (prn) are allowed unless excluded by criteria 5, but such prn use should be reported and documented at each visit.

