10.6.2. Statistical Methodology for Primary Analysis

The primary analysis will use the intent-to-treat methodology and a main-effects model for analysis of covariance (ANCOVA), with adjustment for baseline HbA1c levels. Interaction terms will be examined in supportive analyses. In the event of a significant interaction term, the impact on analysis conclusion will be examined. The primary model will not include interaction terms. Assumptions underlying ANCOVA will be examined. If assumptions of ANCOVA are unwarranted and the validity of the ANCOVA becomes questionable, rank analogues will be advanced as the primary analysis. Multiple imputation (MI) methods will be used to handle missing data.

For completeness, an observed cases analysis will be done by visit in which no data are excluded, no data are imputed, and no data are represented at times other than when they were observed. As an alternative for handling missing data according to the rules of the primary analysis, a supportive analysis will be done using last-observation-carried-forward (LOCF).

For statistical analyses, 95% confidence intervals will be produced for the least squares means (LSM) in each treatment group, as well as the LSM differences as compared to placebo. For MMRM and ANCOVA, two-sided p-values will be displayed for the comparison against placebo.

Suspicious values that appear invalid and outliers that are detected during the blind review of the data will be investigated. Methods for dealing with invalid data and outliers will be defined in the SAP, prior to unblinding. Data considered to be invalid will be set to missing. In general, except for imputation methods specifically described in this protocol, missing data will not be imputed; outliers will not be excluded unless they are considered to be erroneous or invalid values. Sensitivity analyses and exploratory analyses may be done using imputation or excluding invalid data or outliers to ensure robustness of study conclusions.

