6.2.3 Clinical laboratory assessments

Clinical laboratory variables of analysis include raw means and mean changes from baseline for the clinical laboratory measures in this study

- Hematology: hemoglobin, hematocrit, RBC count, platelet count, WBC count, total neutrophils (abs), eosinophils (abs), monocytes (abs), basophils (abs), lymphocytes (abs)
- Clinical chemistry: BUN, creatinine, calcium (total), sodium, potassium, chloride, total carbon dioxide, (bicarbonate), AST (SGOT), ALT (SGPT), alkaline phosphatase (ALK), total bilirubin, direct (conjugated) bilirubin, uric acid, albumin, total protein
- Lipid panel: total cholesterol, HDL-C, LDL-C, triglycerides
- Specialty laboratory tests: HbA1c, C-peptide, lactate, ketones, free fatty acids, GGT, fructosamine, glucagon, 1, 5 anhydroglucitrol.

A treatment-emergent abnormal value (TEAV) is a laboratory analyte that is abnormal after administration of study medication that was not present prior to the administration of study medication.

Safety variables of analysis include:

- Proportions of patients with TEAVs
- Proportions of patients with a TEAV in any liver function test (LFT) including ALT, AST, total bilirubin, alkaline phosphatase.

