7.5 Methodology for Missing Data

In general, for safety, missing data will not be imputed. Missing baseline data will be imputed with the latest available pre-dose value. In the event that no pre-dose value is available, for safety data or for insulin data, the first available data will be used for the baseline comparisons.

In general, for analyses on measures, multiple imputation methodology will be used to accommodate missingness. For dichotomous variables, non-responder imputation is used.

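### SAP 8.3 lets genuine blood pressure, pulse and lipid values recorded after a medication change be set to missing as invalid, so value-based safety summaries may understate a drug effect

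*SAP*

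**What the plan says.** SAP 8.3 (Invalid Data) opens with site queries as the normal route for resolving doubtful data. It then provides a fallback: "in the unlikely event that data from ECG, vital signs, or other data sources are deemed to be highly improbable during blinded data review" "that includes medical, clinical, and data management consensus, invalid will be set to missing". The only illustrations of what qualifies are these: "Examples include pulse rate and blood pressures values when changes in antihypertensive medications have been introduced or changes in lipid measurements in the presence" of altered background lipid medication. No direction, size or time window is attached to the medication change. The conventions are to be set blind and documented.

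The values concerned feed planned safety output. SAP 7.7.3 says "Clinically important values or changes in vital signs will be examined with summary tables and supportive listings", alongside mean change by visit. SAP 6.2.3 lists "Lipid panel: total cholesterol, HDL-C, LDL-C, triglycerides" among the laboratory variables, with raw means, mean changes and proportions with treatment-emergent abnormal values. SAP 14 sets concern thresholds for systolic and diastolic pressure and for triglycerides.

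On what happens to a removed value, SAP 7.5 states: "In general, for safety, missing data will not be imputed". On the trigger, Protocol 6.10.2 asks sites to avoid altering background medication where possible, and adds: "Any changes made to background medications or supplements must be captured in" the patient's CRF.

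**The concern.** The illustrations do not fit the category. A blood pressure taken properly after an antihypertensive was added is neither improbable nor wrong; it is a true value with a known influence on it. Labelling it invalid removes it from the tables meant to detect drug effects on blood pressure and lipids.

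The trigger is also not neutral. A medication change after randomization can be the clinical response to the very worsening, or the very fall, that the safety summary should show. If TTP399 affects blood pressure or lipids, more TTP399 than placebo patients would meet the trigger. Reviewers who do not know the allocation would still remove values unequally, because the imbalance lies in the trigger and not in their judgement.

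Safety and tolerability is the secondary objective of Part 2. Protocol 1.1.4 and SAP 1 both report an earlier trial in type 2 diabetes as free of significant dyslipidemia, so the lipid tables will be read closely.

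**Working it through.** The plan states no figure on this point, so the main check is to set the sections side by side.

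**1. Definition against examples.** SAP 8.3 is about improbable data, yet both examples are of validly measured data. Protocol 10.6.2 pairs invalid with erroneous: "outliers will not be excluded unless they are considered to be erroneous or invalid values". That sentence sits in the efficacy section, so it serves only as a contrast in usage and does not govern safety data.

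**2. Comparison with SAP 8.4.** SAP 8.4 defines an intercurrent event as one after treatment start that prevents observation of the variable or affects its interpretation. A medication change after the start of treatment fits that definition. Laboratory values handled under 8.4 are flagged, moved to a supplementary dataset and examined in a supportive analysis. SAP 8.3 has no such step.

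**3. What can be lost.** In Part 2, vital signs and lipids are measured on treatment at Weeks 2, 6 and 12 (Protocol 8.5 and Appendix 2), and SAP 7.1 keeps follow-up data out of the safety analysis. If medication changes after Week 6, Week 12 is the only later scheduled value. Removing it takes the patient out of the Week 12 mean change, and any first threshold crossing or first lipid abnormality at Week 12 goes uncounted. SAP 14 relies on ECG heart rate and not on vital-sign pulse, so the heart-rate threshold is not affected. Mean pulse is.

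**4. Illustration of size.** All inputs are assumptions except 45 per arm (SAP 1.7, Table 1):
- SD of systolic change 12 mmHg; Week 6 to Week 12 correlation 0.6
- medication changed when the Week 6 rise is at least t = 10, 15 or 20 mmHg
- the change lowers Week 12 pressure by 10 mmHg
- true effect d in the TTP399 arm, 0 in the placebo arm

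For an arm with mean m, let a = (t − m)/12. Then:
- proportion with a medication change = 1 − Φ(a)
- Week 12 mean with post-change values deleted = m − 0.6 × 12 × φ(a)/Φ(a)
- Week 12 mean with treated values kept = m − 10 × [1 − Φ(a)]

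Example, d = 5 and t = 10. Placebo: a = 0.833, 20.2% changed, deleted mean −2.55. TTP399: a = 0.417, 33.9% changed, deleted mean 1.02. Difference with deletion: 1.02 + 2.55 ≈ 3.56 after rounding at the end. Difference with values kept: 5 − 10 × (0.3385 − 0.2023) = 3.64.

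| d | t | Week 12 values lost, placebo / TTP399 (of 45) | Deleted | Kept |
|---|---|---|---|---|
| 3 | 10 | 9.1 / 12.6 | 2.18 | 2.22 |
| 3 | 15 | 4.8 / 7.1 | 2.40 | 2.47 |
| 3 | 20 | 2.2 / 3.5 | 2.61 | 2.70 |
| 5 | 10 | 9.1 / 15.2 | 3.56 | 3.64 |
| 5 | 15 | 4.8 / 9.1 | 3.93 | 4.03 |
| 5 | 20 | 2.2 / 4.8 | 4.28 | 4.42 |
| 8 | 10 | 9.1 / 19.5 | 5.54 | 5.69 |
| 8 | 15 | 4.8 / 12.6 | 6.11 | 6.26 |
| 8 | 20 | 2.2 / 7.1 | 6.68 | 6.89 |

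Deletion hides from 13% (1 − 2.61/3) to 31% (1 − 5.54/8) of the effect, and the loss is unequal by arm in every row. A simulation under the same assumptions agrees within Monte Carlo error. Keeping the treated values raises the estimated difference by only about 0.05 to 0.2 mmHg, because the added drug itself masks the rise. The mean cannot show what treatment has corrected; a count of medication changes by arm can.

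**The case against.** The case for leaving the text alone has real weight.

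- **Removal is discretionary.** It follows a blinded consensus of medical, clinical and data management staff, in an event the SAP calls unlikely. The examples show what may qualify and do not order deletion. This stands, but they are the only guidance reviewers are given, and both point to genuine values.
- **Values, not patients, are removed.** A reader might infer that patients whose condition worsened disappear from the safety comparison. The documents do not support that: the safety set in SAP 4 is everyone dosed, and 8.3 does not alter it.
- **The prompting reading is not named.** The blood pressure and pulse example concerns values once the change has been introduced. A threshold crossed before then still counts, and SAP 8.10 keeps unscheduled readings in the summaries of change to maximum and minimum. This stands, and it limits the loss in threshold counts to first crossings after the change.
- **Other routes exist.** Protocol 9.1 makes a test result leading to significant additional drug treatment a reportable adverse event. Protocol 8.5 and 8.7.2 do the same for clinically significant vital signs and laboratory results after dosing. SAP 7.9 summarizes concomitant medications and SAP 11 plans listings. These routes soften the harm but do not repair the value-based tables, and no by-arm table of antihypertensive or lipid medication changes is specified.
- **Changes may be few.** Eligibility requires stable health and excludes persistent uncontrolled hypertension. This is plausible, but the documents give no rate.

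**Conclusion.** The concern holds in a limited form. SAP 8.3 permits genuine post-change blood pressure, pulse and lipid values to be treated as invalid, with no general imputation and no planned analysis that restores them. By-visit mean changes can then understate a drug effect, as can counts of first systolic, diastolic or triglyceride crossings or lipid abnormalities after the change. Blinding does not prevent unequal loss.

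Two stronger readings are tempting and should be resisted. One is that the signal is hidden: it is not, given adverse event reporting and the retained earlier readings. The other is to size the error by the full untreated rise in each affected patient. That compares deletion with a world in which nobody was treated, whereas the realistic alternative is to keep treated values, and the documents supply neither the number of such patients nor the size of their rises.

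The 13% to 31% range rests wholly on the assumed inputs above and measures deletion and outcome-driven treatment together, against a true effect without added medication. No hypothesis-tested endpoint uses these values. This should be fixed, but it does not threaten the trial's main conclusions.

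**What to change.** Before unblinding:

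1. Delete the two medication-change examples from SAP 8.3 and limit invalid to measurement, transcription or sample errors.
2. Keep every validly measured vital-sign and lipid value in the main safety summaries and threshold counts, whatever the background medication.
3. Flag values recorded after a change in antihypertensive or lipid medication.
4. Tabulate new or changed antihypertensive and lipid medication by arm, next to those summaries. This is essential, because keeping the values alone recovers little.
5. Show the summaries without flagged values only as a sensitivity analysis.

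The cost is a wording edit, one flag, one table of medication changes and the sensitivity display; the changes are already captured under Protocol 6.10.2. The small downside is that the main summaries will include values partly modified by the added drug, which the flag and the sensitivity analysis make visible.
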